3.3.2.1. Efficacy

The evaluated outcomes will be related to two domains: -*How does technology affect the course of the disease*?

Long-term survival

-How technology affects health-related quality of life?

Descriptive analysis of EQ-5D-5L and EORCT QLQ-LC29 questionnaire results by type of approach and surgical procedure

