As regards the analysis of quality of life, the prospective study will take into consideration patients undergoing three types of surgery: robot-assisted, VATS, and open surgery. Specifically, the number of groups enrolled is assumed starting from the average of interventions carried out in the period 2016-2021. Therefore, for the prospective study, we estimated 48 subjects operated with robotic surgery, 94 with VATS, and 258 with open surgery. Literature relating to the comparison of the quality of life in patients operated with VATS and open surgery [38] illustrates the analysis of the EQ-5D questionnaire at different post-intervention time points. The data of our interest relate to the mean and standard deviation of the Visual Analogue Score of the EQ-5D questionnaire administered 4 weeks after the intervention; respectively: VATS 78.1, Open 73.5. The one-way analysis of variance methodology was used to study the power. For robotic surgery, since the necessary data in the literature are not available, we assumed an average of the Visual Analogue Score EQ-5D ranging from 80 to 83, which allowed the calculation of the estimated power illustrated in the table below. A standard deviation of 17.2 was assumed for all three groups based on literature data [38]. For the analysis of statistical power, we used the PROC POWER procedure, statement ONEWAYANOVA of the SAS software (v. 9.4, SAS Institute Inc., Cary, NC, USA).

Mean Visual Analogue Score EQ-5D	Power
80	0.669
81	0.790
82	0.880
83	0.939

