3.3.4.2. Efficacy study

Since this is an observational study, all analyses must take confounding into account. For each outcome, a Direct Acyclic Graph (DAG) will be prepared, discussed by surgeons and epidemiologists, i.e. a graph that allows hypothesizing the causal relationship between intervention and outcome taking into account potential confounding factors, measurable or not. On the basis of this graph, which underlies a causal model, the variables to be included in the multinomial regression model will be selected for estimating the probability of being treated with each surgical modality as a function of potential confounders (known as propensity score). Among the variables that will be considered to define the DAGs are age, gender, performance status, treatment center and tumor characteristics. The inverse of this estimated probability will be used as weight in the regression models (inverse probability weighted, IPW) which will have the outcome as the dependent variable and the treatment modality as the independent variable: robotics, VATS and thoracotomy (reference). Differences in the duration of surgery and hospitalization will be analysed using an IPW generalized linear regression model. The 30-day odds ratio (OR) of death for VATS and robotic surgery versus thoracotomy will be estimated by means of an IPW logistic regression model. Relative survival will be evaluated using a Cox IPW model and expressed both in terms of hazard ratio (HR) and as one and 5 year survival. For inpatient reoperation, the need for conversion to thoracotomy for VATS vs. robotic surgery and major complications by type of surgery, which are expected to be rare events, a we will consider a IPW zero-inflated (Poisson or negative binomial) approach. All estimates will be presented together with 95% confidence intervals obtained from a robust standard error [39]. The same analyses, if allowed by the study number, will be repeated in the three surgical subgroups (atypical and segmental resection, lobectomy, pneumonectomy), in subjects aged less than or equal to 65 years vs. superior, in patients with performance status of 0 vs. 1 vs. 2. Sensitivity analyses will be carried out using alternative models for the probability of estimating the type of intervention.

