3.3.4.3. Quality of life and patient experience

Descriptive analyses will be carried out, also using bar graphs, of the items of the EQ-5D-5L and EORCT QLQ-LC29 questionnaires, comparing the pre- and post-operative values for each surgical approach. Starting from the results of the EQ-5D, the utility index associated with the health-related quality of life (HRQoL) will be calculated, and will be summarized through appropriate measures of position and variability for the three surgical approaches. Differences between surgical approach in terms of utility index will be estimated using a model for longitudinal data weighted by the inverse of the probability of surgical approach, similarly to what is described in the previous paragraph. As regards the PREMs questionnaires, descriptive analyses of the individual items will be carried out globally and by type of treatment.

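### The QLQ-LC29 is listed as an efficacy outcome under a question about the technology's effect, but only the EQ-5D utility index gets a confounding-adjusted analysis between approaches

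*Combined protocol and SAP*

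**What the plan says.** Section 3.3.2.1 (Efficacy) names two domains: long-term survival, and a second headed "How technology affects health-related quality of life". The only analysis it lists for the second is "Descriptive analysis of EQ-5D-5L and EORCT QLQ-LC29 questionnaire results by type of approach and surgical procedure".

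Section 3.3.4.2 (Efficacy study) sets the general rule: "Since this is an observational study, all analyses must take confounding into account". It continues: "For each outcome, a Direct Acyclic Graph (DAG) will be prepared". From that graph come the propensity model and the weights for the outcome regressions.

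Section 3.3.4.3 (Quality of life and patient experience) then treats the instruments differently:

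- Items of the EQ-5D-5L and the QLQ-LC29 are described, "comparing the pre- and post-operative values for each surgical approach".
- The EQ-5D utility index is modelled with propensity weights: "Differences between surgical approach in terms of utility index will be estimated using a model for longitudinal data weighted by the inverse of the probability".
- For the PREMs questionnaire, "descriptive analyses of the individual items will be carried out globally and by type of treatment".

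No section states a weighted or otherwise adjusted analysis of the QLQ-LC29 or of the PREMs.

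**The concern.** The plan asks an effect question about quality of life, states how effect questions must be handled in an observational study, and then leaves the lung-cancer-specific instrument outside that rule. Adjustment reaches the generic utility index only.

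Two things are at stake. First, the plan's own question goes unanswered for the QLQ-LC29, because a within-approach comparison of pre- and post-operative values does not estimate a difference between approaches. Second, three sets of crude summaries will stand next to each other under a heading about the technology's effect, with nothing in the plan to say that they support no comparative conclusion. The introduction already credits the robotic approach with better quality of life, including less pain and faster healing, so a favourable crude pattern could easily be read as support for that statement.

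**Working it through.** No figure in the plan decides this point, so the main check sets the sections side by side.

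| Measure | In the efficacy list (3.3.2.1)? | Analysis by approach (3.3.4.3) | Weighted? |
|---|---|---|---|
| EQ-5D utility index | Yes, through the EQ-5D-5L | Longitudinal model of differences between approaches | Yes |
| QLQ-LC29 | Yes, by name | Item description, pre versus post within approach | No |
| PREMs | No | Item description, overall and by treatment | No |

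**Does the rule reach the QLQ-LC29?** Section 3.3.4.2 covers all analyses and every outcome of the efficacy study. Section 3.3.2.1 names the QLQ-LC29 as an efficacy outcome. Read together, the rule applies, and section 3.3.4.3 does not carry it out.

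**Does the descriptive plan deal with confounding in another way?** Only in part. Section 3.3.2.1 also splits results by surgical procedure, which partly handles the type of resection. Age, performance status, centre and tumour features, all candidates for the causal graphs in section 3.3.4.2, are not handled. Showing pre-operative values reveals baseline differences in score but does not remove differences in expected recovery.

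**Is an adjusted analysis feasible?** Section 3.3.3.3 holds each patient's four questionnaires under one identifier, linked to the administrative variables of Table 4 and the centre variables of Table 5. No new data are needed. Section 3.3.4.2 builds a graph for each outcome, so the weights should come from the graph for the QLQ-LC29 and need not equal those for the utility index.

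**The plan's quality-of-life power figures.** Section 3.3.4.1 gives the group sizes ("we estimated 48 subjects operated with robotic surgery, 94 with VATS, and 258 with open surgery"), EQ-5D visual analogue means of 78.1 (VATS) and 73.5 (open), an assumed robotic mean of 80 to 83, and a standard deviation of 17.2. Assuming two-sided alpha 0.05 (none is stated for this calculation), take the robotic-versus-open contrast in a three-group analysis of variance with 400 − 3 = 397 error degrees of freedom:

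- Standard error = 17.2 × √(1/48 + 1/258) = 17.2 × 0.1572 = 2.70.
- Noncentrality = (robotic mean − 73.5) / 2.70, for example 6.5 / 2.70 = 2.40 at a mean of 80.
- Power at 80, 81, 82 and 83 = 0.669, 0.790, 0.880 and 0.939, exactly the plan's table.

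The table is thus an unadjusted contrast on the visual analogue scale. It says nothing about the QLQ-LC29.

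**What precision would an adjusted QLQ-LC29 comparison have?** The documents give no standard deviation for its scales, so I work in standard-deviation units, at a single time point and with all 400 patients responding. The 95% half-width is 1.96 × √(1/n₁ + 1/n₂) × √d, where d is the variance inflation from weighting. The documents give no d, so 1.25 to 2.0 is an assumed range.

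| Contrast | d = 1 | d = 1.25 | d = 1.5 | d = 2.0 |
|---|---|---|---|---|
| Robotic (48) vs open (258) | 0.31 | 0.34 | 0.38 | 0.44 |
| Robotic (48) vs VATS (94) | 0.35 | 0.39 | 0.43 | 0.49 |

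The intervals are wide, which supports labelling these estimates secondary.

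**The case against.** The best defence is that the plan makes no unadjusted comparison at all. A reader might infer that the QLQ-LC29 and PREMs results are to be formally compared between approaches without adjustment. The text does not support that: no between-approach estimate, test or interval is planned for either instrument, and the only stated QLQ-LC29 comparison is within approach. This part of the defence stands, and the gap is an omission: an effect question with no adjusted answer.

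Four further points stand in whole or part.

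- A reader might infer that the PREMs breach the same rule. They are not in the efficacy or safety lists, the rule sits in the efficacy section, and the PREMs are collected once, at 30 days or the first follow-up visit. For them there is no contradiction, and the longitudinal model does not carry over.
- A reader might infer that the QLQ-LC29 results mix approach with type of resection. The split by procedure largely answers this on paper. With 48 robotic patients the cells will be small, and section 4 withholds results for subgroups of three or fewer.
- The one quality-of-life difference that the plan does estimate is weighted. Section 3.4.3 takes QALYs from the EQ-5D, so no stated economic input comes from the QLQ-LC29 or the PREMs.
- Describing rather than modelling many items with 48 robotic patients can be defended. But the plan does not say that it made this choice, or that the descriptions carry no comparative conclusion.

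**Conclusion.** The point holds for the QLQ-LC29. It is a named efficacy outcome under an effect question, the plan's rule on confounding applies to it, and only unweighted summaries are specified. For the PREMs it is a suggestion only.

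The bias cannot be sized from the documents. A reader might try to do so by assuming an imbalance in some prognostic factor and comparing the result with the 4.6-point difference between VATS and open surgery (78.1 − 73.5). That would not be sound: the plan gives neither the imbalance nor its effect, and the 4.6 points are on the EQ-5D visual analogue scale, a different instrument.

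Nor do the documents support the inference that the primary cost-effectiveness result is at risk. The weakness is confined to the disease-specific quality-of-life answer. The change is worthwhile because it is cheap and because the data and covariates are already to be collected and linked.

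**What to change.** In section 3.3.4.3:

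- Score the QLQ-LC29 into its scales.
- Estimate differences between approaches at days 7 and 30 with the type of IPW longitudinal model already planned for the utility index, with weights derived from the causal graph for this outcome.
- Report 95% confidence intervals and label the results as secondary estimates.
- Keep the item charts as description.

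In section 3.3.2.1, align the wording so that it names the weighted analyses of the utility index and of the QLQ-LC29 beside the descriptive summaries.

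For the PREMs, either present summaries by approach weighted for confounders, or state that they are descriptive and support no comparative conclusion.

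The cost is some added analysis on data already collected, several secondary estimates to report, and wide intervals for every contrast that involves the robotic group.

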3.3.2.2. Safety

- 30-day mortality
- Reoperation during hospitalization
- Need for conversion to thoracotomy for VATS and robotic surgery
- Major complications by type of surgery (Table 3)

Secondly, differences in terms of duration of operation and hospitalization will be evaluated. This information will be used for the cost-effectiveness assessment.

 Table 3 Complications of interest and related ICD-9-CM codes

COMPLICATION	CODE
Iatrogenic cerebrovascular infarction or hemorrhage	997.02
Central nervous system complication (Brain anoxic damage, Cerebral hypoxia)	997.01
Cardiac complications, not elsewhere classified	997.1
(Cardiac: arrest, insufficiency, cardiorespiratory insufficiency, heart failure)	
Post traumatic pulmonary insufficiency	518.5
Urinary complications, not elsewhere classified (Renal: Acute defaillance, acute failure, acute tubular necrosis specified as due to interventions)	997.5
Postoperative infection, not elsewhere classified	998.5x
Hemorrhage or hematoma or seroma complicating a procedure, not elsewhere classified	998.1x
Persistent postoperative fistula	998.6

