The platform of the most used robotic system, the da Vinci, consists of several components: the surgeon's console with a three-dimensional vision system and two manipulators, a surgical cart with one or more arms that execute the surgeon's commands, the Endowrist® instrumentation that allows 7 degrees of movement that simulate and amplify the movements of the human hand and wrist, and a visualization system with 3D endoscopes that allows an enlargement of the image in real time. The absence of the tactile function is a significant problem that developers are trying to overcome with the technological innovation of haptic feedback, which allows the surgeon to "feel" the reaction of the tissue or organ to the force exerted [18]. Intuitive surgical, the leading manufacturer of robotic surgery platforms, estimates that over 5 million minimally invasive robotic procedures have been performed since 2000, with nearly 5000 units installed worldwide (https://www.intuitive.com/en-us). After the introduction of the da Vinci platform in Italy in 1999, there were 111 robots active in our county in 2019; of those 22 placed in Lombardy region [19]. To use the robotic platform, specific training is required. Usually, it is provided by the manufacturer and distributor and is addressed to both the surgeon and all operating room personnel, also involving anesthesiologists and sterilization personnel [19]. In the area served by the ATS of Milan, the Training School in Robotic Surgery of the Department of Health Sciences of the State University of Milan was recently established. The robotic lung-thoracic surgery system comes alongside open surgery and video-assisted thoracoscopy (VATS). VATS is a minimally invasive approach that does not require classic thoracotomy. VATS instrumentation includes optics in addition to classic thoracic or laparoscopic instruments [20]. Minimally invasive surgery (both robotic and VATS) has several benefits over open

surgery, such as a lower risk of infection and a lower healing and recovery time, while maintaining overlapping efficacy outcomes [21]. Robotic surgery ensures a greater degree of flexibility compared to the laparoscopic approach, it allows to operate even in hard-to-reach locations, uses instrumentation with greater stability and allows a very precise three-dimensional view [2].

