However, the cost of the necessary equipment is relevant; the purchase cost is about 1.7 million euros, while the annual maintenance represents about 10% of this sum. In addition, we have to add the costs

for disposable material and equipment with limited reusability (usually ten procedures). Consequently, the cost of this technology is high and volume dependent [4]. The European Society of Medical Oncology (EMSO) also highlights the fact that the robotic approach can be more expensive than the commonly used VATS [22]. On the other hand, in the robotic approach other costs are reduced, such as those related to hospitalization, the occupation of intensive care units, and the treatment of complications, which are reduced. Furthermore, there are potential advantages such as reduction of blood loss and tissue trauma, and less need for surgery conversion to open surgery compared to VATS. Furthermore, from the patient's point of view, there is an improvement in the quality of life (less pain, faster healing with consequent rapid return to work, less burden on caregivers). Lastly, this method has the advantage of improving ergonomics and reduce the physical effort of the surgeon [23]. Previous studies have attempted to evaluate the cost-effectiveness profile of this method in the thoracic area. Camberlin's study [4] is an HTA report carried out by the Belgian agency KCE, whose economic evaluation consists of a literature review for cost evaluation and a budget impact analysis. This study highlights that the cost structure of the different surgical approaches is very different and difficult to compare and the studies are generally of low quality. However, the analysis of the studies points out that robotic surgery is more expensive than traditional approaches such as thoracotomy and VATS. The systematic review by Turchetti [24] draws the same conclusion, while focusing on further relevant aspects: the facilitation in the execution of complex and advanced operations and the different role of the assistant surgeon during robot-assisted thoracoscopy operations. The organizational aspect most addressed in the literature was instead the training course for the use of the robotic surgical platform [19].

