3.3.3. Collected variables

3.3.3.1. From administrative databases

The staff of the Epidemiology Unit involved in the study will extract the information specified in Table 4 from the current administrative databases of the ATS of Milan. Subsequently, it will perform the deterministic record linkage on a unique key (fiscal code) and will anonymize the dataset for the analysis, removing the tax code, deleting the dates once the time intervals necessary for the analysis have been calculated (age, length of hospitalization, length of post-operative stay, etc.), and assigning a random ID to the patient. Separate copy of correspondence between social security number and random id will be kept in a separate password protected file.

Data flow	Data relating to	Variables
Hospital Discharge	Patient	Civil status, study level
Summary (SDO)	Hospital admission	Admission date, intervention date, discharge date, type of discharge, within hospital transfers
	Diagnoses and complications	All ICD-9-CM diagnosis codes present in a SDO
	Procedures	DRGs, ICD-9-CM procedure codes, procedure date
Patient registry	Patient	Sex, birth date, city of residence, vital status at 2022/12/31
SDO, outpatient services, pharmaceuticals, exemptions	Patient comorbidities	Charlson comorbidity index calculated through the algorithm in use at the Epidemiology Unit
Cancer registry	Cancer	Histology (morphological code ICDO3, margins of resection, number of mediastinal lymph nodes removed, number of positive mediastinal lymph nodes, stage at diagnosis)

Table 4 Variables collected from administrative databases

3.3.3.2. From the data provided by the centers through a dedicated platform made available by the ATS of Milan

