3.3.4. Data analysis

3.3.4.1. Power of the study

To study the efficacy, data from the retrospective and prospective study will be analyzed jointly. For the retrospective part, approximately 5,000 patients operated on for lung cancer in the participating centers from 01/01/2016 to 12/31/2021 will be included. Based on the average of approximately 450 subjects operated on in the participating centers over 6 months during the years 2019-2021, a sample of 400 subjects eligible for enrollment in 6 months during 2022 was considered in the prospective observational study. As regards the statistical power in the analysis of the primary efficacy outcome, i.e. long-term survival, the calculation was based on an assumption of non-inferiority. The following formula was used to calculate potency in survival studies which is based on the hazard ratio [37].

$$1-\beta=\Phi(z-z_{1-\alpha}), z=(\ln(\theta)-\ln(\theta_0))\sqrt{np_Ap_Bp_E}$$

Where:

- θ_0 = hazard ratio under the null hypothesis, set equal to 1
- θ = observed hazard ratio
- pE = probability of event, i.e. death, set equal to 0.8 on the basis of epidemiological data from the ATS cancer registry
- pA = proportion of treated by robotic surgery equal to 0.12 on the basis of the data present in the SDOs for the year 2019 and of the preliminary information provided by the participating centers

pB = 1-pA

- n = sample size, equal to 5400
- Φ = distribution function of the standard normal
- A = I-type error, set equal to 0
- $1-\beta =$ statistical power

By varying the observed HR of VATS death versus the observed control group between 1.08 and 1.15, the statistical power ranged from 0.5 to 0.91. The power calculation was performed using R (v4.1.2, R Core Team 2021, Vienna, Austria.)

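### Reoperation is compared between approaches only until discharge, so if stays differ the comparison can depart from equality at equal 30-day risk, by an amount and in a direction the documents do not fix

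*Combined protocol and SAP*

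**What the plan says.** Section 3.3.2.2 gives four safety items, one of which is "Reoperation during hospitalization". Death, in the same list, is counted to 30 days. The section adds that "differences in terms of duration of operation and hospitalization will be evaluated".

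Section 3.3.4.2 keeps the in-stay window and assigns an inverse-probability-weighted zero-inflated count model: "For inpatient reoperation, the need for conversion to thoracotomy for VATS vs. robotic surgery and major complications by type of surgery". It states no exposure time, offset or censoring at discharge. The weights come from a model of the choice of approach. The candidate variables named for it include age, gender, performance status, centre and tumour characteristics.

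The background in section 1 expects advantages that may shorten stays. It credits minimally invasive surgery with benefits "such as a lower risk of infection and a lower healing and recovery time", and says that "in the robotic approach other costs are reduced, such as those related to hospitalization". Neither statement gives a number of days by approach.

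Table 4 in section 3.3.3.1 already takes "DRGs, ICD-9-CM procedure codes, procedure date" from the hospital discharge records (SDO), along with admission and discharge dates. The same section deletes dates once the intervals needed for analysis have been calculated. Its examples do not include the time from operation to reoperation.

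**The concern.** Discharge happens after treatment and may depend on it. If one approach sends patients home earlier, its patients have less time in which a reoperation can be counted. A reoperation on day 6 counts for a patient still in hospital but not for a patient who was discharged on day 5 and readmitted. Two approaches with the same 30-day risk can then show different in-stay risks.

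Weighting balances factors that precede the operation. It does not equalise an observation window that closes at a post-operative event.

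What is at stake is how one safety comparison is read. The in-stay count would be correct as a count. It could mislead if taken as the relative safety of the approaches over the post-operative month.

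**Working it through.** The plan states no risk, sample size or power for reoperation, so there is no figure to reproduce. The calculation below shows what the in-stay window can do when the true 30-day risks are equal.

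**Inputs from the documents.** The total sample is 5,400 and the robotic share 0.12 (section 3.3.4.1). For the prospective part, "we estimated 48 subjects operated with robotic surgery, 94 with VATS, and 258 with open surgery", out of 400. Applying these shares to the whole sample gives 0.12 × 5,400 = 648 robotic and 258/400 × 5,400 = 3,483 open.

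**Assumptions, none of them in the documents.** Stays are 5 days (robotic) and 8 days (open). Reoperation times follow the same exponential distribution in both groups, with half-life h of 1 to 7 days. A share r of the events that would have fallen after discharge occurs in patients kept in hospital, and so is counted.

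**Formulas.**
- Cumulative share of events by day t: F(t) = 1 − 2^(−t/h).
- Share of 30-day events after a stay of L days: s = 1 − F(L)/F(30).
- Apparent risk ratio: RR = [1 − s_R(1 − r_R)] / [1 − s_O(1 − r_O)], with R robotic and O open.

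**Worked case, h = 7.** F(5) = 0.390, F(8) = 0.547 and F(30) = 0.949. Hence s_R = 1 − 0.390/0.949 = 0.59 and s_O = 1 − 0.547/0.949 = 0.42. With no retention, RR = 0.390/0.547 = 0.71.

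**Equal retention, 5 against 8 days.**

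| Retained in both groups | h = 1 | h = 2 | h = 3 | h = 5 | h = 7 |
|---|---|---|---|---|---|
| None | 0.97 | 0.88 | 0.81 | 0.75 | 0.71 |
| 25% | 0.98 | 0.91 | 0.87 | 0.83 | 0.82 |
| 50% | 0.99 | 0.94 | 0.91 | 0.90 | 0.90 |
| 75% | 0.99 | 0.97 | 0.96 | 0.95 | 0.95 |

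**Smaller differences in stay, half retained.** 6 against 8 days gives 0.99 to 0.93, and 7 against 8 gives 1.00 to 0.97. Equal stays with equal retention give 1.00.

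**Unequal retention, 5 against 8 days, h = 7.**
- None retained robotic, half open: (1 − 0.588)/(1 − 0.423 × 0.5) = 0.52.
- Half retained robotic, none open: (1 − 0.588 × 0.5)/(1 − 0.423) = 1.22.

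So the longer-stay approach can also be the one that looks better.

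**Scale against sampling error.** At an assumed 4% risk the expected events are 25.9 and 139.3, so SE(log RR) = √(1/25.9 + 1/139.3) = 0.214 before weighting. For 5 against 8 days with equal retention, the shift over the five half-lives is:
- 0.13 to 1.58 SE with none retained;
- 0.10 to 0.94 SE with 25%;
- 0.06 to 0.52 SE with half;
- 0.03 to 0.22 SE with 75%.

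If weighting doubled the variance (SE 0.303), the upper ends for none and half retained would fall to 1.11 and 0.37 SE.

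**The case against.** The strongest reply is that nothing here is an error. The outcome is named as an in-hospital count in both sections, consistently, and no text presents it as a 30-day measure. It is one of four safety items. The power section names "the primary efficacy outcome, i.e. long-term survival", and nothing in the plan names reoperation as an input to the cost-effectiveness ratio. This stands, and it is why the severity is low.

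The second reply is that every condition for a bias lies outside the documents. The larger values need many late events: the 0.71 above has 59% of robotic and 42% of open 30-day reoperations falling after the assumed discharge day, with nobody kept in for a developing problem. This also stands. It does not make the effect vanish at moderate retention, however, since 25% retained still gives 0.82 at h = 7.

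A reader might infer that the plan will make robotic surgery look falsely safe. The documents do not support that. Section 1 gives a direction for recovery and hospitalization costs but no stays, and unequal retention can reverse the direction of the ratio.

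The third reply is that a 30-day count brings its own misclassification, because no reoperation codes are given and planned second procedures must be separated out. That is a real cost, but no reason to leave the windows unequal. Annex 2 is not shown and may define the variable further.

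**Conclusion.** The point holds in a conditional form. The reoperation window closes at discharge, discharge may differ by approach, and the planned weighting does not equalise the window. If stays differ and some reoperations occur after discharge, the in-stay comparison can depart from 1.00 at equal 30-day risk.

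Neither size nor direction can be fixed from the documents. Under the assumed stays, half-lives and equal retention, the apparent ratio lies between 0.99 and 0.71; unequal retention widens this to between 0.52 and 1.22 at a half-life of 7 days. These are illustrations, not estimates for this study. The effect is absent with equal stays and equal retention, and small if nearly all reoperations are early.

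Severity is low: the outcome is declared, consistent and secondary, and the change is a cheap improvement. The conclusion reads hospitalization as the index stay, which the wording in section 3.3.4.2 supports.

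**What to change.** In sections 3.3.2.2 and 3.3.4.2, define the comparative outcome as reoperation within 30 days of the operation date, in the index stay or any later admission, from linked SDO procedure codes and dates. Then:
- calculate the operation-to-reoperation interval before dates are deleted under section 3.3.3.1;
- extract SDO records to at least 30 days after the last operation;
- state in advance which procedure codes count and how planned second procedures are separated;
- keep the in-stay count as a secondary description.

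With a common window and complete capture, equal 30-day risk gives a ratio of 1.00 whatever the stays.

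The cost is edits to two sections, one derived interval, and a code list and planned-procedure rule that must be built, with some misclassification. The count of facility accesses over 6 months in section 3.4.3 serves costing and does not itself supply procedure-level readmissions, so these must be extracted. Reoperations without an admission would still be missed. Later admissions not held in the ATS SDO database may be missed too, in both the retrospective and the prospective parts: section 3.1 requires only the index stay to be there. The documents do not say how many that would be.
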